#### 10.5.4.2.2. Secondary Safety Endpoints

- **Devices related serious adverse events within 90 days of follow up**  
The number and percentage of subjects with device related SAEs will be summarized. The number of events will also be summarized. Device relatedness will be adjudicated by an independent CEC.
- **sICH at 24h post procedure specified according to the Heidelberg Bleeding Classification (HBC)**  
sICH at 24 hours post procedure as specified by HBC will be assessed by an independent CEC. The number and percentage as well as the two-sided 95% confidence intervals around the percentage will be summarized.
- **NIHSS at 24h post procedure**  
The observed NIHSS total score at 24 hours post-procedure and changes from the baseline score will be summarized.
- **90 Day All-Cause Mortality**  
All-cause mortality at 90 days post-procedure will be summarized. Two-sided exact 95% confidence intervals will be constructed around the percentage.

#### 10.5.5. Health Economic Endpoints

Hospitalization data will be analyzed using the mITT population:

- **Hospitalization length of stay for index procedure and unscheduled re-hospitalizations**

The mean, median, minimum and maximum duration of hospitalization length of stay will be summarized for subjects who have been treated with study device during index procedure. The number and percentage of subjects with hospitalization length of stay in the 0-1 day, 1-2 days and >2 days categories will be summarized for the index procedure.

- **Healthcare resource utilization for index procedure, post-procedure and re-hospitalizations for unscheduled events**

The number and proportion of subjects with re-hospitalizations post index procedure, and the number of re-hospitalizations after the index procedure will be summarized for subjects who have been treated with study device.

#### **10.5.6. Clot Analysis**

Clot data assessed by the independent Clot analysis lab will be summarized using the mITT population.

Composition of clot components to be evaluated includes: Red Blood Cells (RBC), White Blood Cells (WBC), platelets, fibrin and other fibrous proteins. Clot composition along with weight and area data will be summarized per pass and overall.

#### **10.5.7. Plans for Interim Analyses**

Interim analyses will be conducted for regional (outside Europe, as well as for European MDR) regulatory submission purposes. Only descriptive statistics will be reported. Results of the interim analyses will not be used as a basis for stopping the trial early.

#### **10.5.8. Handling of Missing Data**

All data will be summarized as observed, no missing data will be imputed in the study unless specified elsewhere.

### **10.6. Measures to Minimize Bias**

Cerenovus will be diligent in controlling for bias by utilizing proper study design and implementation of the approved study protocol. EC approval will be obtained at all clinical sites prior to study initiation. Study agreements/contracts will be made with the hospitals/universities and all compensation for conduct of the study will be paid to the hospitals/universities and not to the investigators. Inclusion and exclusion criteria will be implemented to avoid selection bias.

An independent Clinical Events Committee (CEC) will review and adjudicate the safety endpoints, as specified in the CEC charter. CEC members will provide an impartial review and will not hold a financial interest in Cerenovus. An independent core laboratory will perform the angiographic assessments for the primary and secondary effectiveness

endpoints. These evaluations will be performed by an independent reader who does not hold a financial interest in Cerenovus.

Clinical outcomes will be measured in a standardized manner using the National Institutes of Health Stroke Scale, a standardized, objective, clinical assessment tool used to quantify and document the neurological status of patients and to act as a predictor for clinical outcomes. It is used to determine stroke and the severity of stroke.

Clinical outcomes will be measured in a standardized manner using the Modified Rankin Scale, a commonly utilized seven-point scale measuring functional outcome and disability in patients with stroke. The mRS measures independence and dependence related to activities of daily living and can be used over time to determine recovery or regression. In this study, 90 day mRS evaluations will be conducted by an independent evaluator who is not part of the interventional treating team, the patient's direct clinical care or involved in data entry (e.g., neurologist CRNC).

An independent CEC will review and adjudicate safety endpoints to determine whether they meet protocol-specified criteria. CEC members will provide an impartial and standardized review of these safety events.

An independent Imaging Core Lab will perform the angiographic assessments for the primary effectiveness endpoint, as well as the secondary effectiveness endpoints that are based on imaging. The Imaging Core Lab will provide an impartial and standardized review of imaging outcomes.

Study monitors will have clinical research experience and be proficient at study monitoring. Study data will be source data verified (SDV) as specified in the monitoring plan using the subject's medical records, study source worksheets, clinic notes, and radiographic reports as applicable as source documentation.

In order to minimize potential bias, subject screening logs will be maintained at the sites. These will document all first-line aspiration mechanical thrombectomies performed at the site. All cases of EMBOVACTM being used in stroke treatment, will be taken into account for total screening numbers, noting why the potential subject was not enrolled.

## **11. Ethics and Protection of Human Subjects**

### **11.1. Ethical Standard**

As the Sponsor of this study, Cerenovus has the overall responsibility for the conduct of the study and, is conducted in accordance with GCP, ISO 14155 requirements, local regulations, the signed clinical study contract with Sponsor, the protocol outlined herein, as well as with the principals of the Declaration of Helsinki.

- **General Responsibilities**

Sponsor's general duties consist of assuring that sites have received EC approvals, selecting investigators, ensuring proper clinical site monitoring and ensuring subject informed consent is obtained. Any additional requirements imposed by an EC or regulatory authority shall be followed, if appropriate.

- **Data Quality and Reporting**

Sponsor is responsible for providing quality data that satisfy applicable regulations and informing proper authorities of unanticipated adverse effects and deviations from the protocol as applicable.

- **Selection of Investigators**

Sponsor will select qualified investigators, obtain a signed Investigator Agreement and provide the investigators with the information necessary to conduct the study.

- **Supplemental Applications—Protocol Amendments**

As appropriate, Sponsor will submit changes in the study protocol to investigators to obtain EC re-approval. A justification for each amendment will be documented.

- **Maintaining Records**

Sponsor will maintain copies of correspondence, device and procedure related Serious Adverse Events and other records related to the study. Sponsor will maintain records related to the signed Investigator Agreements.

## **11.2. Ethics Committee (EC)**

The protocol, informed consent form, recruitment materials, and all participant materials will be submitted to the EC for review and approval. EC approval of both the protocol and the consent form must be obtained before any participant is consented.

Any amendment to the protocol will require review and approval by the EC before the changes are implemented to the study. Cerenovus and the EC must approve in writing any changes to the protocol that affect the rights safety and/or welfare of the subjects or may adversely affect the validity of the study. All changes to the consent form will be EC approved and a determination will be made regarding whether previously consented participants need to be re-consented.

Investigators are responsible for submitting and obtaining initial and continuing review of the study by their EC.

### **11.3. Informed Consent and Data Release Form Process**

#### **11.3.1. Consent and Other Informational Documents Provided to Participants**

Subject's informed consent must be obtained and documented according to the principles of informed consent. Due to the emergent nature of AIS, consent may be obtained up to 45 days post-procedure, as permitted by the local regulations and EC.

The 45-day window of consent is a mid-point in the patient's follow-up and will prevent study bias for the following reasons:

- Due to the nature of AIS and its treatment, subjects may require several weeks to regain the capacity to provide their consent to be part of the study or to physically sign the informed consent form
- Due to precautionary restrictions at hospitals to prevent the spread of infectious disease, it is not always possible for the treating physician to request the subject's LAR/relative to provide informed consent on the subject's behalf. The 45 day consenting window gives the physicians more chances to connect with subject's relatives

In the event that a subject is not capable of giving their informed consent, all reasonable efforts will be made to obtain informed consent from the subject's LAR (for example, relative or caregiver). This includes cases where the subject dies during the intervention or shortly thereafter, before they can provide their informed consent, or when the severity of the subject's condition prohibits them from providing informed consent. This will vary from case to case, depending on the status / mental state of the patient or if the patient is in life threatening condition at the time of screening. In this case, the investigators should follow their standard practice to determine if a patient is able to provide their own consent or whether consent should be obtained from a patient's LAR.

The EC must review and approve an informed consent form (ICF) specific to this study. Cerenovus will provide each study center with an example ICF or data release form. The clinical center, to meet specific EC requirements, may modify this example ICF. The original, subject's ICF must be retained by the investigational site for monitoring, and a copy provided to the subject.

If applicable per local regional requirements, a data release form must be obtained prior to releasing subject information. The EC must review and approve the data release form specific to this study and the written data release form must be signed and dated by the subject prior to participation in this study. The original, signed and dated data release form must be retained by the investigational site for monitoring, and a copy provided to the subject.

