### **7. Study Schedule**

#### **7.1. Pre-Screening / Screening**

Subjects presenting with AIS to enrolling medical treatment facilities will be evaluated and treated by the physician according to the institutional practice prior to enrollment in the study. All assessment and imaging performed for this study are part of SOC for stroke treatment. Informed consent is mandatory and must be obtained before any data is captured in the eCRF.

A subject can be consented to participate in this study from the point of imaging confirming a large vessel occlusion up to 45 days post-procedure. During the eligibility screening, the investigator or designee will perform an initial evaluation of potential study subjects according to the inclusion/exclusion criteria. Post-procedure, the eligibility criterion to be confirmed will be the requirement for the EMBOVAC™ aspiration catheter and ADAPT to be attempted to be used in the first 3 passes, if required, unless evolution of care is required to remove a clot in a distal vessel of <2mm in diameter, and confirmation that all assessments were in alignment with the schedule of assessments (See Table 1 Schedule of Assessments).

For subjects in whom consent is sought, the investigator, or designee, will explain the research study to the subject and answer any questions that may arise. The possible risks and possible benefits of participation will be discussed. The subject will be asked to read, review and sign the EC approved informed consent form. The informed consent process is detailed further in Section 11.3.

All subjects screened will be documented on the Screening/Enrolment log, including the reason for non-participation for subjects who do not enroll.

If for any reason the subject does not meet the eligibility criteria when assessed by the investigator for inclusion in the study, the subject will not be considered enrolled in this study or be followed per this clinical protocol.

All subjects who provide informed consent will be entered into eCRF regardless of whether or not they participate in the study.

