7.5.2.2 Secondary Safety Endpoints

Device-related SAEs and all-cause mortality, Kaplan-Meier analysis (using product limit estimates) will be applied. Kaplan-Meier event rate and its associated two-sided 95% CIs using log-log transformation will be reported, the estimate of standard error will be computed using Greenwood's formula.

- **Devices related serious adverse events (SAEs) within 90 days of follow up as determined by an independent Clinical Events Committee**

Kaplan-Meier analysis will be performed to analyze the device related SAE rate within 90 days. Device related SAEs are considered as events; where the event date is the date of first event. Subjects without events will be censored at the date of last contact. The event rate at 90 days with associated 95% CIs will be provided. Device related SAEs beyond 90 days will be listed.

- **sICH at 24h post procedure specified according to the Heidelberg Bleeding Classification (HBC) as determined by an independent Clinical Events Committee**

sICH at 24 hours post procedure as specified by HBC will be assessed. The number and percentage of subjects with events will be summarized with CIs.

- **NIHSS at 24h post procedure**

The observed NIHSS total score at 24 hours post-procedure and changes from the baseline score will be summarized.

- **90 Day All-Cause Mortality**

Kaplan-Meier analysis will be performed to analyze all-cause mortality within 90 days. All-cause mortality is considered as the event; where the event date is the date of mortality. Subjects without events will be censored at the date of last contact. The event rate at 90 days with associated 95% CIs will be provided. Deaths beyond the 90 days will be listed.

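### 90-day mortality is biased low unless patients who die before consenting are enrolled as often as survivors; the 45-day consent window does not prevent this, and no planned output measures it

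*Protocol*

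**What the plan says.** **Consent and enrolment.** Protocol 11.3.1: "consent may be obtained up to 45 days post-procedure, as permitted by the local regulations and EC". It presents the window as a mid-point in the patient's "follow-up and will prevent study bias for the following reasons". The two reasons are time for patients to regain capacity and more chances to reach relatives. Nothing may be entered in the eCRF before consent (Protocol 7.1), and data go to the sponsor only with it (Protocol 6).

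**Deaths before consent.** For patients who cannot consent, Protocol 11.3.1 says "all reasonable efforts will be made to obtain informed consent from the subject's LAR", and adds: "This includes cases where the subject dies during the intervention or shortly thereafter, before they can provide their informed consent". The same section says that, because of infection-control restrictions, "it is not always possible for the treating physician to request" a representative's consent.

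**Who counts as enrolled.** Protocol 7.3 accepts consent from the subject or a legal representative. Protocol 8.2.4 and SAP 5 refer only to the subject signing. Where a data release form applies, Protocol 11.3.1 requires the subject's signature before participation. Protocol 7.1 also makes eligibility depend on "confirmation that all assessments were in alignment with the schedule of assessments".

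**Analysis.** Both analysis sets contain enrolled subjects only (Protocol 10.2, SAP 5). SAP 7.5.2.2: "Kaplan-Meier analysis will be performed to analyze all-cause mortality within 90 days". SAP 7.1 sets the index procedure as Day 0.

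**Screening log.** Under Protocol 10.6, every stroke case treated with EMBOVAC "will be taken into account for total screening numbers, noting why the potential subject was not enrolled". The SAP plans no analysis of the log.

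**The concern.** The cohort is defined by an event, consent, that can fall as late as day 45, while the mortality clock starts on day 0. A patient who survives can be approached for weeks. A patient who dies on day 3 can enter only if a representative is found and agrees. If that happens less often, early deaths drop out of numerator and denominator together and the curve is too low.

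The protocol's two reasons do not answer this. Regaining capacity describes people who live long enough to recover. More time to reach relatives helps, but does not show that early deaths are captured as fully as survivors.

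No planned output would reveal a shortfall. SAP 7.2 summarises consented subjects and the analysis sets, and the sensitivity analyses in SAP 7.11 concern mRS only. Because interim results are intended for regulatory submissions (Protocol 10.5.7, SAP 7.9), an unmeasured downward tilt in mortality matters even in a descriptive study.

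**Working it through.** **The plan's own figure.** The only computed figure is the margin of error for the primary endpoint: 1.96 × √(0.8 × 0.2 / 95) = 8.04%, which agrees with the stated 8.0%. It does not bear on mortality; the plan gives no expected mortality rate.

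**Inputs.** From the documents: consent up to day 45, procedure as Day 0, enrolled subjects only, no delayed entry described. Assumed, because the documents are silent: true mortality, the share of deaths before consent, and how often those patients are enrolled.

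**Worked example.** Take 100 eligible treated patients, 20 deaths by day 90, 12 of them before consent would have been given, everyone else enrolled, follow-up complete. If *u* of the 12 are not enrolled, observed mortality is (20 − u)/(100 − u).

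| Share of the 12 not enrolled | u | Observed mortality |
|---|---|---|
| 0% | 0 | 20/100 = 20.0% |
| 25% | 3 | 17/97 = 17.5% |
| 50% | 6 | 14/94 = 14.9% |
| 75% | 9 | 11/91 = 12.1% |
| 100% | 12 | 8/88 = 9.1% |

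The last row is what a literal reading of the signature wording in Protocol 8.2.4 and SAP 5 would give, since a patient who dies before signing could never be enrolled.

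**General form.** Let M be true mortality, f the share of deaths before consent, and c the enrolment probability of those patients relative to everyone else. With complete follow-up the expected estimate is M(1 − f(1 − c)) / (1 − M f(1 − c)). It equals M when c = 1 and is below M for any c < 1.

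- Check against the table: M = 0.20, f = 0.6, c = 0.5 gives 0.14/0.94 = 14.9%.
- M = 15%, f = 50%: 15.0%, 13.4%, 11.7%, 9.9% and 8.1% for c = 1, 0.75, 0.5, 0.25 and 0. The bias runs from 0 to −6.9 points.
- c = 0.5, f from 30% to 70%: 8.6% to 6.7% for M = 10%; 13.0% to 10.3% for M = 15%; 17.5% to 14.0% for M = 20%; 22.1% to 17.8% for M = 25%.

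**Simulation.** With M = 15%, deaths weighted early, consent times uniform over days 0 to 45 and 61% of deaths before consent, Kaplan-Meier from the procedure gave 6.4%, 10.9% and 15.0% for c = 0, 0.5 and 1. With entry delayed to consent it gave 14.2% at c = 0. Delayed entry is not a full remedy here, because a subject enrolled through a representative after death has an entry time later than the event.

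**Why adding back deaths gives an upper bound.** Suppose 6 of the 12 early deaths are enrolled, and 75% of the other 88 (6 of 8 later deaths, 60 of 80 survivors). Observed mortality is 12/72 = 16.7%. Adding the 6 unenrolled early deaths gives 18/78 = 23.1%, above the true 20%, because the unenrolled survivors stay out of the denominator.

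**The case against.** The strongest reply is that the protocol foresaw the problem. Protocol 11.3.1 extends representative consent to patients who die during or soon after the intervention, Protocol 7.3 counts that as enrolment, and Protocol 11.3.2 leaves room for alternatives such as consent by telephone before a witness. Compared with a shorter window, 45 days should lose fewer severely affected patients. Mortality is a secondary, descriptive endpoint, and the primary endpoint is read at the end of the procedure.

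Most of this stands, and it rules out three stronger readings that a reader might infer:

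- *That the mortality estimate is certainly biased.* It is not if early deaths are captured as fully as survivors, and the capture rate is unknown.
- *That a survivor enrolled on day 30 contributes 30 days in which death was impossible.* A patient who dies on day 15 can still be enrolled through a representative. The issue is unequal capture, not guaranteed event-free time.
- *That a patient who dies before the 24-hour visit fails the schedule check in Protocol 7.1.* Exclusion criterion 1 concerns assessments already undergone that deviate, and Protocol 11.3.1 expressly envisages enrolling patients who die during the intervention. The wording needs clarifying, no more.

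The reply does not rescue the claim of prevention. The representative route carries no capture target, its limits are conceded in the same section, and other sections contradict it. Logging cases under Protocol 10.6 controls nothing unless the log is reported.

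**Conclusion.** The point holds conditionally. Mortality counted from the procedure in consented subjects is biased low unless c = 1, and nothing in the documents secures or measures c. The direction follows from the design; the size does not. The range of 20% down to 12.1% rests on an assumed 20% mortality, 12 of 20 deaths before consent and 0% to 75% of those not enrolled.

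A reader might also infer that mRS 0-2, sICH and device-related SAEs are shown to be tilted. They share the consent condition and could move the same way to the extent that they go with early death, but no figure here or in the documents demonstrates it. The claim of prevention should be corrected, the enrolment definitions reconciled and the remaining selection reported.

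**What to change.** 1. **Protocol 11.3.1:** replace the claim of prevention with a statement that the window reduces selection on survival but does not remove it.
2. **Enrolment wording:** bring Protocol 8.2.4, the data release text in Protocol 11.3 and SAP 5 into line with Protocol 7.3, so that representative consent counts as enrolment, as far as local rules allow. State in Protocol 7.1 that an assessment precluded by death is not a departure from the schedule.
3. **SAP table from the screening log:** all EMBOVAC-treated patients by reason for non-enrolment, with death before consent as its own category, and the number enrolled through a representative after death. Use aggregate counts as local rules permit, since individual data may not be shared without consent. The documents do not say that the log identifies deaths, so the category should be specified.
4. **SAP sensitivity analysis:** report 90-day mortality in enrolled subjects, and again with unenrolled, otherwise eligible deaths added to numerator and denominator. Label this an upper bound, noting that it relies on a complete log and on patients unenrolled for other reasons not dying more often than the bounded rate.

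A split of outcomes by time of consent would not help, because consent time itself depends on severity and survival; if shown, it should be descriptive only.

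The cost is some text changes, one extra table and a less favourable bounded mortality figure. Treatment and follow-up are unchanged.
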